#### **7.4 SAFETY MONITORING AND REPORTING**

If any serious and unexpected AEs occur during the study, all PIs will be notified by the Sponsor within 72 hours of learning of the event.

### **8.0 PRODUCT COMPLAINTS**

#### **8.1 PRODUCT COMPLAINT DEFINITION**

A product complaint is defined as any written, electronic or oral communication that alleges deficiencies related to the identity, labeling, quality, durability, reliability, safety, effectiveness, or performance of a device after it is released for distribution (21CFR 820.3 (b)). A product complaint may or may not be associated with an AE/SAE.

#### **8.2 REPORTING PRODUCT COMPLAINTS**

All product complaints related to devices in the procedure shall be documented throughout the clinical investigation.

Product complaints related to an Ethicon-manufactured circular stapler must be reported to the Sponsor in a timely manner and no later than 24 hours after becoming aware of the event. When a sponsor representative becomes aware of a product complaint, the Product Complaint Team must be notified within 24 hours after becoming aware of the event. The Product Complaint Form must be emailed to the Sponsor Customer Complaint team at the following email address:

[REDACTED]  
[REDACTED]

One copy of the processed form should be kept on-site and the device should be retained. Sponsor representatives will organize collection of the device for evaluation as needed.

## 10.0 APPENDIX I: SPONSOR CONTACT INFORMATION

## 11.0 APPENDIX II: ANTICIPATED ADVERSE EVENTS

| Associated with left-sided colon resection and General Anesthesia |   |
|--|---|
| Air/Gas Embolism   | Ischemia                                      |
| Abcess   | Jaundice                                      |
| Adhesions  | Leak  |
| Anastomotic Leak   | Lethargy                                      |
| Bleeding   | Leukocytosis                                  |
| Bowel obstruction  | Liver Failure                                 |
| Bradycardia  | Mesenteric Infarction                         |
| Cardiac Arrhythmia   | Mesenteric Ischemia                           |
| Constipation   | Myocardial Infarction                         |
| Deep Venous Thrombosis   | Nausea  |
| Dehydration  | Nutrient Deficiency                           |
| Diarrhea   | Obtundation, Depressed Level of Consciousness |
| Disseminated Intravascular Coagulation (DIC)                             | Oliguria                                      |
| Coagulopathy   | Pain (increased/severe/chronic)               |
| Discharge of feces through drain   | Peritonitis                                   |
| Dizziness  | Pneumonia                                     |
| Electrolyte Imbalance  | Pulmonary Embolism                            |
| Dysphagia  | Renal Failure                                 |
| Evisceration   | Respiratory Failure                           |
| Headache   | Respiratory Insufficiency                     |
| Fistula  | Stenosis                                      |
| Headache   | Stricture                                     |
| Hematuria  | Systemic Inflammatory Response                |
| Hemorrhage   | Tachycardia                                   |
| Hypernatremia  | Thromboembolic Event                          |
| Hyperphosphatemia  | Thrombosis                                    |
| Hypertension   | Transient Ischemic Attack (TIA)               |
| Hypotension  | Tightness of the chest, Angina                |
| Hypoxia  | Urinary Retention                             |
| Incisional Hernia  | Urinary Tract Infection (UTI)                 |
| Ileus  | Volume Depletion, Hypovolaemia                |
| Infection / wound infection  | Vomiting                                      |

## Revision History

Revision Number	Revision Date	Reasons for Revision
1.0	28JAN2020	Original Document
2.0	05FEB2020	Addition of Adverse Event tables to support the submission to NMPA for registration in China. These include differentiation of intraoperative (day of surgery) versus postoperative (strictly after surgery) and are described in mock-up Tables 29 to 33. Additional text has also been added to Section 8.5 to describe these tables.

# 1 Introduction

This is the Statistical Analysis Plan (SAP) for the final analysis of data collected under Protocol ESC-16-002. This SAP describes in detail the statistical methodology and statistical analyses for this protocol.

## 1.1 Study Objectives

The primary objective of this study was to prospectively evaluate the intra-operative performance of the powered circular stapler in a post-market setting using the ECHELON CIRCULAR™ Powered Stapler device per its Instruction For Use (IFU). Secondary objectives include surgeon workload, surgeon satisfaction, and proactive surveillance of safety of the powered circular stapler used in left colectomy procedures in a post-market setting.

## 1.2 Study Design

This was a prospective open-label, multi-center clinical study designed to evaluate the intra-operative performance of the powered circular stapler in left colectomy procedures in a post-market setting. Investigators were to perform the procedure using the device in compliance with their standard surgical approach and the ECHELON CIRCULAR™ Powered Stapler IFU.

Each site utilized consecutive screening and enrollment in an effort to generate a random and representative patient population sample. Patients satisfying the entry criteria will be consented and screened. Subjects will be considered enrolled at the time of the first attempted anastomosis using the ECHELON CIRCULAR™ Powered Stapler device during their procedure. Procedures were performed either open or via minimally invasive surgery (MIS) according to institutional standard-of-care (SOC). Use of a hand port and robotic assistance were permissible providing the powered circular stapler was used to create the anastomosis. Conversion from MIS to open surgery is permissible under the protocol at the surgeon's discretion for the patient's safety. Follow-up care was documented post-operatively to confirm healing of the anastomosis. The final scheduled study visit was to occur 28 days post-procedure (routinely scheduled follow-up with the surgeon). Follow-up by phone for subjects was allowed when an on-site visit is not planned or was more than six weeks post-operative.

A total of 165 eligible subjects were planned to be enrolled in up to 12 sites (United States and Europe) to ensure at least 150 subjects complete the study. The planned maximum number of subjects enrolled at any site was not to exceed 20% of the total number of subjects enrolled in the study.

## **2 Treatment Assignment**

This was a prospective, open label, single-arm study where all enrolled subjects were to have the ECHELON CIRCULAR™ Powered Stapler device utilized for anastomosis of left-sided colon resection. The original design of this study planned to have two treatment arms including commercially available manual staplers and the powered circular stapler. Enrollment was to be sequential within each site where manual cases would be performed first and then transitioning to enrollment of powered cases. As part of amendment 3 to the study protocol, a business decision was made to move to a single-arm study for expeditious trial completion. The objective of the study was revised and the planned comparison of the manual stapler to the powered stapler was removed. The objective of the study was restated to evaluate the intra-operative performance of just the powered stapler. The study design herein is described as a single-arm study. Prior to this amendment, a total of 22 subjects had been enrolled and had procedures performed with a manual circular stapler. Data from these subjects has been maintained in the study database and this data is included in the listings generated as part of the final analysis for this study.

## **3 Randomization and Blinding Procedures**

This was a single-arm, open-label study. No randomization occurred and no blinding procedures were required.

## **4 Interval Windows**

Interval windows are not defined for the purpose of analysis in this study outside of the visit windows that are provided in the Schedule of Assessments in the final protocol. There will be no assigning of observations to time points outside of the visit to which they are recorded in the electronic Case Report Forms (eCRFs) and data collected in Unscheduled Visit forms will be listed as such.

## **5 Levels of Significance**

No hypotheses are specified for this study and no p-values are being calculated, therefore no level of significance is specified. All estimation of endpoints will be performed using 95% confidence intervals.

## **6 Analysis Sets**

The summary of safety and effectiveness endpoints will be performed on the set of enrolled subjects in whom an anastomosis was attempted with the ECHELON CIRCULAR™ Powered Stapler. This will be labeled the Full Analysis Set. This set of subjects will be identified by having answered “Yes” to the question “Was anastomosis attempted?” on the Intraoperative Data eCRF.

The summary of effectiveness endpoints will be repeated on the set of subjects in the Full Analysis Set who also have no major protocol deviations. This will be labeled the Per Protocol Set.

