## **5.6 ANALYSIS SETS**

The primary analysis of safety and effectiveness endpoints will be performed on the Full Analysis Set, defined as all subjects who are enrolled in the study and have an anastomosis attempted with the powered circular stapler. A Per Protocol analysis set will be defined as all subjects who had an anastomosis completed with the powered circular stapler and no major protocol deviations. Effectiveness analyses will be repeated for the Per Protocol Set.

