### **Handling of Dropouts or Missing Data**

All analyses will be performed only on subjects undergoing the surgical procedure (colorectal anastomosis attempted with a powered circular stapler) and only observed data will be analyzed. There will be no imputation of missing data for any parameters or for early terminated subjects.

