## 8.4 Primary and Secondary Endpoints and Associated Hypotheses

### 8.4.1 Primary Endpoint and Associated Hypotheses

No formal hypotheses are specified for this study. The study endpoints are representative of endpoints that are currently reported in the available literature for stapler performance and this will allow for qualitative comparisons with the results from this study.

The primary performance endpoint in this study is the percentage of subjects who experienced a failure of the ECHELON CIRCULAR™ Powered Stapler to perform per its IFU. This includes but is not limited to difficulty placing or removing the stapler, stapler misfire/failure of the device to fully fire, staple line defects, incomplete or thin donuts, tissue damage, positive intraoperative leak test, detached components, unformed staples, or any other device failures.

The denominator for the primary endpoint will be the total number of subjects where an anastomosis was attempted and the numerator will be the number of subjects who experienced a stapler performance issue. An exact 95% confidence interval using the Clopper-Pearson method will also be estimated.

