### 8.7 Handling of Missing Data

All summaries will be performed only on enrolled subjects and only observed data will be summarized. There will be no imputation of data for early terminated subjects or for missing data within the database.

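### The Full Analysis Set is defined by powered-stapler attempts but selected by an eCRF item that names no device, in a database that also holds 22 manual-stapler subjects

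*SAP*

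**What the plan says.** SAP section 6 first describes the Full Analysis Set as enrolled subjects with an attempted anastomosis using the powered stapler. It then says how the set is found in the data: "This set of subjects will be identified by having answered “Yes” to the question “Was anastomosis attempted?” on the Intraoperative Data eCRF". Protocol 5.6 gives the same concept, "defined as all subjects who are enrolled in the study and have an anastomosis attempted with the powered circular stapler", and Protocol 5.8 (Handling of Dropouts or Missing Data) adds a general limit: "All analyses will be performed only on subjects undergoing the surgical procedure (colorectal anastomosis attempted with a powered circular stapler".

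SAP section 2 explains that the study began with two arms and became single-arm under amendment 3. It reports: "Prior to this amendment, a total of 22 subjects had been enrolled and had procedures performed with a manual circular stapler". Those records stay in the study database, and "this data is included in the listings generated as part of the final analysis for this study". The SAP does not expressly say that these subjects are left out of the summary tables.

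Three other places bear on who is counted:

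- SAP 1.2 defines enrolment by device: "Subjects will be considered enrolled at the time of the first attempted anastomosis using the ECHELON CIRCULAR™ Powered Stapler device during their procedure".
- SAP 8.7 sets the scope of all summaries without a device: "All summaries will be performed only on enrolled subjects and only observed data will be summarized".
- SAP 8.4.1 sets the primary denominator: "The denominator for the primary endpoint will be the total number of subjects where an anastomosis was attempted". Table 7 footnote [1] says the same in substance. Neither names the stapler.

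**The concern.** An analysis-set rule should return the defined set when it is programmed as written. Here the definition has two conditions (an attempt, and the powered device) and the rule has one. If every subject in the database had a powered stapler, the second condition could be left implicit. SAP section 2 says that is not so.

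The word enrolled does not close the gap. SAP 1.2 ties it to a powered attempt, while SAP section 2 applies it to the manual subjects. SAP 8.7, which limits summaries to enrolled subjects, inherits that ambiguity.

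The Full Analysis Set carries the primary endpoint (Table 7) and the adverse event tables (Tables 11 to 16 and 29 to 33); the last group was added for a registration submission. The SAP's Per Protocol Set is no backstop. It requires only Full Analysis Set membership and no major deviation, whereas Protocol 5.6 requires an anastomosis completed with the powered stapler. A selection error would therefore carry into Table 18.

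**Working it through.** **Rule against definition**

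| Place | Attempt required | Powered device required |
|---|---|---|
| Protocol 5.6 and 5.8 | Yes | Yes |
| SAP 6, definition | Yes | Yes |
| SAP 6, selection rule | Yes | Not stated |
| SAP 8.4.1 denominator; Table 7 footnote [1] | Yes | Not stated |
| SAP 8.7 | Through enrolled | Only if enrolled has the SAP 1.2 meaning |

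The Table 6 shell has separate rows for whether an anastomosis was attempted and for the type of stapler used. Stapler type therefore appears to be recorded apart from the attempt item, and the rule uses only the attempt item.

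**Inputs**

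- 165 planned subjects and an expected issue rate of 15% to 20% (SAP section 7).
- 22 manual subjects (SAP section 2).
- Clopper-Pearson 95% intervals (SAP 8.4.1).
- Assumptions: 165 powered subjects are reached, all 22 manual subjects have a Yes on the same item, and the flag alone is programmed.

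**The plan's own figures.** The one-sided 95% margin is 1.645 × √(p(1 − p)/165). It is 4.57% at p = 0.15 and 5.12% at p = 0.20, which agrees with the stated 5.1% after rounding. The chance of at least one event at a 1.5% rate is 1 − 0.985^165 = 0.917, which agrees with the stated figure of more than 90%. Neither depends on the point at issue.

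**Size of the set.** 165 + 22 = 187. The manual share is 22/187 = 11.8%. The Table 6 stapler-type counts would sum to 165/187 = 88.2% of N, because the shell lists only the two powered staplers.

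**Effect on the primary rate, manual issues also counted.** Shift = (22/187) × (manual rate − powered rate), or 1.18 points per 10-point difference, and zero when the rates are equal. For illustration, the 15% to 20% range is applied to the manual cases: 3.3 to 4.4 of 22, taken as 3 or 4 events.

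| Powered only (95% CI) | Manual issues | Pooled (95% CI) | Shift, points |
|---|---|---|---|
| 25/165 = 15.15% (10.05–21.55) | 3 | 28/187 = 14.97% (10.19–20.91) | -0.18 |
| | 4 | 29/187 = 15.51% (10.64–21.51) | +0.36 |
| 33/165 = 20.00% (14.19–26.92) | 3 | 36/187 = 19.25% (13.86–25.64) | -0.75 |
| | 4 | 37/187 = 19.79% (14.33–26.23) | -0.21 |

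The documents do not give the issue rate in these 22 subjects. The arithmetic limits, from 0 to all 22 with an issue, are -1.8 to +10.0 points from 15.2% and -2.4 to +9.4 points from 20.0%.

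**Effect if only powered-stapler failures are counted over the any-device denominator.** The rate is multiplied by 165/187 = 0.882. Then 25/187 = 13.37% (8.84–19.10), a fall of 1.78 points, and 33/187 = 17.65% (12.47–23.88), a fall of 2.35 points. This is the largest fall the pooling could produce.

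**The case against.** The best reply is that the rule should be read with the sentence before it. It refers back to a set already limited to enrolled powered-stapler subjects, so the eCRF item may only separate attempted from not attempted within that set. The surrounding text supports this:

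- Protocol 3.1 and 3.2 and SAP 1.2 define enrolment by a powered attempt.
- Protocol 3.6 treats consented patients without a powered attempt as screen failures.
- Protocol 5.8 limits all analyses to powered attempts.
- SAP section 2 can be read as history when it calls the manual subjects enrolled, and it sends their data to the listings.
- Table 6 has rows for powered staplers only, and Table 9 is titled for the powered device.

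The eCRF is not in the documents and may itself carry the device. On the consistent reading the shifts are small beside intervals roughly 11 to 13 points wide, and pooling would show up in Table 6.

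Most of this stands. The intent is clear, a programmer following it would exclude the 22, and nothing shows that any result was affected. What it does not answer is that the stated means of identification omits a condition of the definition, that the primary denominator omits it too, and that the SAP never expressly excludes the 22 from summaries. The correct set is reached by inference from other sections, not from the rule.

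**Conclusion.** The concern holds as a minor fault: the selection rule in SAP section 6 does not carry out its own definition. Confidence in the mismatch is high. Confidence that a reported result would change is low to moderate, because that requires the 22 to share the eCRF item, to have answered Yes, and to be selected by the flag alone.

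If all three occurred with 165 powered subjects, just under an eighth of the set would be manual cases. The primary rate would move by less than one point if the manual issue rate lay near the SAP's literature range, and by more only if manual and powered rates differed widely or manual cases were counted in the denominator alone. The study is descriptive with no hypothesis test, and the planned sample size and stated precision are unaffected.

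**What to change.** In SAP section 6, select the Full Analysis Set by two conditions: a Yes on the attempted-anastomosis item, and the circular stapler used or attempted was the ECHELON CIRCULAR powered stapler, taken from the recorded stapler or device data. Word the device condition so that powered attempts that were not completed stay in; Table 6 has a row for such cases. Use the same wording in SAP 8.4.1 and Table 7 footnote [1]. Add one sentence stating that the 22 manual-stapler subjects appear in listings only, which also settles what enrolled means in SAP 8.7.

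The cost is one added condition, matching wording in one section and one footnote, one sentence, and one line in the analysis-set program. Table 6 indicates that stapler type is already recorded, so no new data are needed. If the program already filters by device, the change only documents it. As a check on any output, the Table 6 stapler-type counts should account for the whole Full Analysis Set, apart from missing values.

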## 7 Sample Size Justification

A total of 165 eligible subjects was planned to be enrolled in up to 12 sites to ensure at least 150 subjects complete the study. No formal hypothesis was being tested in this study, thus the sample size was not statistically sized, but rather was considered sufficient for a descriptive summary of stapler performance issues through confidence interval estimation and evaluation of safety. The sample size of 165 subjects was consistent with the amount of information that was planned to be collected on the powered stapler in the original study design and provides acceptable precision for estimation of the rate of stapler performance issues. Available literature suggests that stapler performance issues are observed in 15% to 20% of subjects in whom a circular stapler is used, and a sample size of 165 subjects will provide a margin of error for a one-sided 95% confidence interval that does not exceed 5.1% for estimation of the true rate of stapler performance issues.

Further, in consideration of rare AEs that may occur, for an event that occurs at a rate of, for example, 1.5%, then in a sample of 165 subjects, the probability of observing at least 1 event is greater than 90% under a binomial probability model. Thus, this sample size provides a high probability of observing rare events if they do occur and provides reasonable assurance that the absence of such events in the study is not a result of too few subjects being studied, should none be observed.

## 8 Analyses to be Conducted

### 8.1 General Conventions

Subject data will be summarized in tables and presented in further detail in listings. All eCRF data will be listed per subject for all subjects. Descriptive statistical analyses will be provided for pre-specified study endpoints. Summaries for continuous variables will include a minimum of number of observations (n), mean, standard deviation, median, minimum, and maximum. Summaries for categorical variables will include number and percentage.

Analyses will be conducted using SAS software. During the course of programming of tables that are mocked up in this SAP, minor modifications may become necessary. Examples of these minor modifications include, but are not limited to, re-wording of a footnote, addition of a footnote, re-labeling of a column, or addition or removal of a column from a listing. In cases where modifications to tables or listings are not related to a change in statistical analysis methodology or conclusions that could be made on the originally proposed methodology, then no amendment of the SAP is necessary. Any final analyses that differ from what has been specified in this document will be identified within the final statistical output and documented within the clinical study report.

## 8.2 Disposition of Study Subjects

Subject disposition will be summarized using counts and percentages. The number and percentage of subjects in the Full Analysis Set who completed and discontinued will be tabulated along with the specific reasons for discontinuation.

## 8.3 Demographic, Baseline, and Surgical Characteristics

Summary statistics of subject demographics (age, gender, race, height, weight, body mass index, and ethnicity) and pre-operative surgical characteristics (bowel preparation and administration of antibiotics) will be presented for the Full Analysis Set. Medical History (ASA score, surgery indication, level of anastomosis, clinical stage, and smoking history) will be summarized in a similar manner. Surgical characteristics including procedure duration, splenic flexure mobilization, surgical approach, anastomosis details, stapler used, and conversion to open will also be summarized.

